### 2.3. Primary outcome measures

Participants gave blood and stool samples a day before intervention with barley beta-glucans. Blood sampling was performed for insulin resistance determination and for lipid profile determination (Total cholesterol, HDL-cholesterol, LDL-cholesterol, triglycerides). They also had option to give a blood sample for genetic investigation of genes associated with lipid metabolism (apoE).

Analysis were performed in accordance with health community centres in Ajdovščina and Ljubljana, Slovenia. Venous blood samples were obtained by professional medicine personnel for analysis of fasting glucose, lipids and insulin.

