#### 2.3.3. Faecal sampling and DNA isolation

Faecal samples were collected one day before the start and at the end of the intervention. The samples were frozen immediately and stored at -20 °C until use. DNA was isolated within one week after sampling. DNA isolation was performed in parallel using the protocol for isolation of DNA from faecal samples described by Yu and Morrison (2004) [9].

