#### 2.3.4. Microbial community analysis

**DGGE:** PCR-DGGE fingerprinting was performed to check the quality of isolated DNA between parallel samples and to compare the individual profiles. PCR-DGGE analysis was performed as described by Matijašić et al. (2014) [10].

**Real-time PCR analysis** was performed by an established procedure for quantification of bacteria in faecal samples [10] with slight modifications using a ViiA™ 7 Real Time PCR System (Applied Biosystems, USA). Data were analysed with ViiA™ 7 Software 1.2.2 (Applied Biosystems, USA).

**Next generation pair end sequencing:** For 16S rRNA sequencing, 23 participants were chosen randomly among those with both samples qualified for sequencing after DGGE examination. In total, 46 samples from 14 persons in the test group and nine persons in the control group were examined.

The Illumina Miseq platform with v.3 2x300 pair end technology was used for sequencing V3 and V4 16S rRNA regions (Microsynth). After demultiplexing, raw reads were processed following the UPARSE pipeline (Usearch v.8, June 2015) [11]. Stringent quality filtering based on a low expected number of errors was used for OTU formation with algorithm parameters optimized after mock sample analysis (34 strains). With relaxed quality filtered sequences, more than 91 % of raw reads could be placed into an OTU with a 0.03 distance criterion. Presumptive OTU identity was determined with the 'usearch\_global' function searched against Silva NR SSU v.119 and LTP SSU type strains v.121 database. Taxonomy was assigned to OTUs with Wang et al.'s (2007) [12] method implemented in Mothur v.1.35 and the RDP training set 14 [13]. FastTree2 was used for the generation of an approximately maximum-likelihood phylogenetic tree [14]. Taxonomy, the OTU table and the phylogenetic tree were handled with the 'R' package Phyloseq for statistical analysis and graphics [15].

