## 2.4. Secondary outcome measures

After 4 weeks of dietary intervention protocol of primary outcome measures was repeated.

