## 3. STATISTICS

For analysis of participants' anthropometric and metabolic characteristics, RT-PCR results and microbial richness and diversity measures, a Wilcoxon signed-rank test or paired samples *t*-test were used as appropriate with  $P < 0.05$  for significance and  $P < 0.1$  for reporting a trend (SPSS v.21). Statistical sequence analysis was based on differential abundance testing using the 'R' package DESeq 2 [16]. Differential abundance that occurred in test group subjects after dietary intervention but not in the control group was determined in a model with interaction (time, group and subject). Significance was reported for  $P < 0.05$  after multiple inference correction (Benjamini-Hochberg), and all OTUs with  $P < 0.05$  before correction were screened for trends. Initial microbial abundance differences between test group subjects who responded to dietary intervention with a 10 % plasma total cholesterol concentration drop and those without reduction were also tested with Deseq2 [16]. OTUs with  $P < 0.1$  after correction were considered significant. Alpha and beta diversity measures and PCoA of weighted UniFrac distances were calculated and plotted with Phyloseq [15].

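### The responder analysis compares baseline OTUs within the test arm only, so a listed OTU cannot be attributed to response to beta-glucans

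*SAP*

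**What the plan says.** SAP section 3 (Statistics) describes two DESeq2 analyses of OTUs.

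- **Change over time.** "Differential abundance that occurred in test group subjects after dietary intervention but not in the control group was determined in a model with interaction" with terms for time, group and subject. Significance is corrected P below 0.05, by Benjamini-Hochberg.
- **Responder contrast.** Initial abundance in "test group subjects who responded to dietary intervention with a 10 % plasma total cholesterol concentration drop and those without reduction were also tested". OTUs with P below 0.1 "after correction were considered significant".

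SAP section 2.3.4 limits the sequence data: "46 samples from 14 persons in the test group and nine persons in the control group were examined". For stool, section 2.3.3 says: "Faecal samples were collected one day before the start and at the end of the intervention". Total cholesterol is in the lipid profile of section 2.3, and section 2.4 adds: "After 4 weeks of dietary intervention protocol of primary outcome measures was repeated". The lipid table in Protocol section B also has a before and an after column for total cholesterol.

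**The concern.** The first group is described as having responded to the intervention. All that is observed is a fall in total cholesterol while eating the test bread. Some people would show such a fall on control bread. An OTU related to cholesterol change in general (a prognostic OTU) would then separate the two groups just as an OTU that modifies the effect of beta-glucans would. Multiplicity correction does not help, because the association is real and only its interpretation is wrong.

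A reader could take the listed OTUs as markers of who benefits from beta-glucans, when the randomised comparison that could support this was not used. The word *significant* also has two meanings for OTUs in one paragraph, without a reason.

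**Working it through.** **1. Does any part of the plan supply the comparator?** The interaction model asks whether OTU abundance *changes* differently between arms. The responder contrast asks whether *baseline* abundance goes with later cholesterol change. The first does not answer the second, and no other section has a baseline OTU by group term or repeats the contrast in controls.

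**2. Are the data there?** (14 + 9) participants x 2 samples = 46, which reproduces the SAP's figure. By design the nine sequenced controls have baseline stool and total cholesterol before and after. A comparison is therefore possible without new data.

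**3. Can a 10% fall occur without beta-glucans?** The documents give no within-person coefficient of variation (CV), so 4 to 8% is assumed. With independent errors at two visits and no mean change, the percent change has SD of about √2 x CV, and P(fall of at least 10%) = Φ(−10 / (√2 x CV)).

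| CV | √2 x CV | P | Expected among 14 |
|---|---|---|---|
| 4% | 5.66 | 3.9% | 0.5 |
| 6% | 8.49 | 11.9% | 1.7 |
| 8% | 11.31 | 18.8% | 2.6 |

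A simulation that also selects baseline values of at least 5.0 mmol/L (population mean 5.5 or 6.0, SD 0.9 or 1.0, all assumed) gives 3 to 4%, 12 to 13% and 20 to 21%. In it, these chance fallers start 0.3 to 0.5 mmol/L above those with no fall.

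**4. Who is in neither group?** Read literally, people with a fall between 0 and 10% are in neither. With an assumed CV of 6% and mean fall of 4% (SD 8.49):
- fall of at least 10%: Φ(−6/8.49) = 0.240, or 3.4 of 14;
- no fall: 1 − Φ(4/8.49) = 0.319, or 4.5 of 14;
- in between: 1 − 0.240 − 0.319 = 0.441, or 6.2 of 14.

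**5. How often would a prognostic OTU be flagged?** Same setting: 14 subjects, independent normally distributed OTUs, two-group t-tests rather than DESeq2, Benjamini-Hochberg at 0.1, and one OTU with correlation r to cholesterol change unrelated to beta-glucans.
- Among 100 OTUs: about 0.3% (r = 0.3), 1.9% (0.5) and 7.3% (0.7). Repeat runs move these by a few tenths of a point, so I carry about 0.3 to 7.5%.
- Among 500 OTUs: 0.2%, 0.5% and 2.3%.
- About 15% of runs have fewer than two subjects in a group and count as not flagged.
- r = 0.7 is a ceiling for an OTU acting through the baseline value if all change is within-person noise. That correlation cannot exceed 1/√2 = 0.71.

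**6. What does 0.1 instead of 0.05 do?** With no true association, the chance of listing at least one OTU is about 10% against 5% among usable runs.

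**7. Could the between-arm test replace the contrast?** For one true OTU among 100, the Benjamini-Hochberg 0.05 working level is about 0.05/100 = 0.0005. Take slopes fitted per arm and compared with Welch degrees of freedom, at 14 + 9, with the OTU related to change in the test arm only (SD of change 8.5 to 12 points in the test arm, 8.5 in controls, assumed). Power at 0.0005 is then 0.6 to 1.1% (r = 0.5) or 2 to 4.5% (r = 0.7). As a screen it would find almost nothing.

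**The case against.** The strongest reply is that the SAP claims little. It defines the responder group in the same sentence, so nobody is misled about who was compared. It does not say that baseline microbiota predicts response to beta-glucans. A reader might infer that from the wording, but the text stops at testing for differences. A within-arm association can be reported as exploratory. This stands, and it reduces the point to labelling and interpretation. It does not remove it: the SAP does not call the analysis exploratory, it declares OTUs significant, and its label for the group is causal.

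A 10% false discovery rate is also a legitimate, disclosed choice for a separate question. That stands too. Calling the 0.1 level an error would go too far; what is missing is a reason and consistent wording. The section's opening sentence treats P below 0.1 only as a trend, but that rule is for other tests and is not stated to be after correction.

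Regression to the mean is possible, not shown. Table 1 requires total cholesterol of at least 5.0 mmol/L, but people already diagnosed with metabolic syndrome entered directly, and the documents do not say whether the screening value served as baseline. Within-person variation and the participants' usual diet, which section 2.2 says they kept, are enough for the argument.

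**Conclusion.** The point holds, as a minor one. The responder contrast has no comparator, so it cannot separate an OTU that goes with cholesterol change in general from one linked to response to beta-glucans. That follows from the design and needs no simulation. The size does depend on assumptions the documents do not supply: CV, mean fall, number of OTUs, strength of association, and linear tests in place of DESeq2. Under those assumptions a single prognostic OTU among 100 is flagged about 0.3 to 7.5% of the time after correction.

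Two stronger readings are not supported. The documents do not show that the listed OTUs are spurious or merely prognostic, only that the analysis cannot tell. Nor do they prove that the 10% cut and the 0.1 level were chosen after seeing data. The SAP's Introduction says it was written once the trial was complete, so prespecification cannot be shown from it, but an earlier dated plan may exist.

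The three hypotheses in section 1.2 do not depend on this analysis, so the trial's main conclusions are untouched.

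**What to change.** **Wording.**
- Describe the first group as having had a fall of at least 10% in total cholesterol, and drop the statement that they responded to the intervention.
- State where participants with a fall of 0 to 10% go.
- Label the analysis exploratory, and post hoc unless an earlier dated plan exists.
- Give the reason for 0.1, or describe these OTUs as listed at a 10% false discovery rate.

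**Analysis.** For each listed OTU, show the same association in the nine sequenced controls. Report the between-arm difference in the slope of cholesterol change on baseline OTU abundance (stated transformation, all 23 participants, separate residual variance per arm) with a confidence interval. Keep cholesterol change as the outcome. In the reverse regression the slope is cov(OTU, change) / var(change), so it differs between arms whenever the variance of change does, even for an OTU with the same effect in both.

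**Interpretation.** Do not attribute an OTU to response to beta-glucans unless the between-arm difference supports it. That support is necessary but not sufficient, because the OTUs were picked on test-arm data and the interval does not allow for this. Do not read a null difference as evidence of no difference.

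**Cost.** A text change and a small re-analysis of data already held. Some listed OTUs will lose their interpretation. If nothing is re-run, the wording changes and one sentence saying that the contrast cannot be attributed to beta-glucans are the minimum.

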### 1.2. Hypothesis

1. 4- week consumption of beta-glucans alters the composition of intestinal microbiota and changes the ratio of different bacteria groups and consequently effects production of short chain fatty acids in a population with metabolic syndrome or with high risk for metabolic syndrome development.
2. 4- week consumption of beta-glucans has an influence on glucose metabolism and consequently improves insulin resistance within people with metabolic syndrome or with high risk for metabolic syndrome development.
3. 4 - week consumption of beta-glucans improves specific plasma lipid content in a population with metabolic syndrome or with high risk for metabolic syndrome development.

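### SAP section 3 names no between-arm test of overall microbiota composition: beta diversity is only plotted, and the one between-arm microbiota test is OTU by OTU in 14 v 9 people

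*SAP*

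**What the plan says.** - **Hypothesis.** SAP section 1.2, item 1, states that beta-glucan consumption "alters the composition of intestinal microbiota and changes the ratio of different bacteria groups", with an effect on short-chain fatty acids as a consequence.
- **Sequenced subset.** SAP section 2.3.4 states that "23 participants were chosen randomly among those with both samples qualified for sequencing after DGGE examination", and that "46 samples from 14 persons in the test group and nine persons in the control group were examined".
- **Overall composition.** SAP section 3 closes with "PCoA of weighted UniFrac distances were calculated and plotted with Phyloseq". No test of the distances is named, within or between arms.
- **Before-after tests.** The same section covers, along with the anthropometric and metabolic data, "RT-PCR results and microbial richness and diversity measures, a Wilcoxon signed-rank test or paired samples" *t*-test. RT-PCR is not stated to be limited to the 23 sequenced people.
- **Between-arm test.** A change in OTU abundance seen in the test arm but not in the control arm "was determined in a model with interaction (time, group and subject"), using DESeq2. Significance is declared "after multiple inference correction (Benjamini-Hochberg"). OTUs with uncorrected P < 0.05 are screened as trends only.
- **Timing.** SAP section 1 says that the document was written once the trial had been completed.

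**The concern.** Hypothesis 1 is first of all a claim about the community as a whole. The randomised comparison that answers it asks whether composition changed more, or differently, in the test arm than in the control arm. SAP section 3 has a measure suited to that question, the weighted UniFrac distance, but stops at a plot.

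A PCoA plot has no error rate, and it does not by itself account for two samples coming from each person. Separation by chance can look real, and a real shift can be hidden by the differences between people. The OTU analysis asks a different question, namely which taxa changed. A small change spread over many taxa may leave no single OTU past the corrected threshold. The trial could then report no significant OTUs beside a suggestive plot, with nothing formal to connect the two.

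**Working it through.** **1. The plan's own figure.** Two samples per person: 2 × (14 + 9) = 46, as stated. The documents give no sample size, power, effect size or OTU count for the microbiota outcome, so there is nothing else to reproduce.

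**2. What each stated analysis covers.**

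| Measure | Test in SAP section 3 | Compares arms? | Addresses overall composition? |
|---|---|---|---|
| Weighted UniFrac, PCoA | none; plotted | no | yes |
| Richness and diversity | paired, before-after | no | not as composition: variety can stay constant while the taxa change |
| RT-PCR | paired, before-after | no | targeted groups only |
| DGGE profiles | none named | no | in part |
| OTU abundance | DESeq2 interaction, corrected | yes | one OTU at a time |

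No row has both a between-arm test and overall composition. The term for diversity measures in the first sentence of section 3 is not defined. A paired test fits alpha diversity, but even if beta diversity were meant, the test would still be before-after.

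**3. Before-after tests do not fill the gap.** Assume the same true change of 0.5 SD in both arms, with 14 and 9 people. The paired *t*-test then has power of 41 % and 26 %. The pattern of significance in the test arm only has probability 0.41 × (1 − 0.263) = 0.30, with no difference between arms.

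**4. Is a between-arm community test feasible?** The number of ways to assign arm labels is C(23, 9) = 817,190. The smallest attainable P-value is 1/817,190 ≈ 1.2 × 10⁻⁶, so the label count is no obstacle.

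**5. What 14 v 9 can detect.** For one summary of change per person, use a two-sided 5 % *t*-test with 21 df and non-centrality d × √(14 × 9/23) = 2.34 d. Power of 80 % needs d = 1.26; power at d = 0.8 is about 43 %. This is a guide only, not the power of a distance-based test.

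**6. OTU tests against an omnibus test (simulation).** Each person has one change score per OTU, normal with SD 1. The OTU analysis is a *t*-test per OTU with Benjamini-Hochberg correction at 5 %. The omnibus statistic is the sum over OTUs of the squared difference in arm means, with its P-value from permuting arm labels across people. OTU number, share shifted, size of shift and correlation are all assumptions. For the second row, two separate sets of runs gave 13 % v 87 % and 17 % v 88 %.

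| Setting | Any corrected OTU finding | Omnibus P < 0.05 |
|---|---|---|
| 300 OTUs, no shift | about 5 % | about 5 % |
| 300 independent, 30 % shifted by 0.4 SD | 13–17 % | 87–88 % |
| 300 independent, 10 % shifted by 0.4 SD | about 8 % | about 27 % |
| 300, correlation 0.3 within blocks of 30, 30 % shifted by 0.4 SD | about 16 % | about 41 % |
| 300 or 1,000 independent, 10 % shifted by 1.26 SD | 99–100 % | about 100 % |

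The gain from an omnibus test is thus confined to small, widespread shifts, and it shrinks when OTUs move together.

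**The case against.** The strongest reply is that the plan already contains a proper between-arm analysis. The DESeq2 model includes subject, time and group, so it respects the pairing and compares change between arms. Its declared findings are corrected for multiplicity. A significant interaction OTU would itself be evidence that composition changed differently between arms. All of this stands. What it leaves open is the case in which no single OTU crosses the threshold.

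Several stronger readings are tempting, and the documents do not support them:

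- *There is no community-level test at all.* Richness and diversity are community-level summaries and are tested, though only before-after.
- *Hypothesis 1 rests only on OTU tests in 23 people.* RT-PCR results are tested too, and are not said to be confined to those 23.
- *The OTU tests have only 5 to 10 % power against a diffuse shift.* At d = 1.26, power is about 10 % at a threshold of 0.05/300 and 5 % at 0.05/1,000. That is the strictest Benjamini-Hochberg step, which applies when a single OTU is affected. When many OTUs shift, the threshold relaxes, and at that size with 10 % of OTUs shifted some finding is almost certain.
- *Conclusions are drawn from the plot.* Section 3 says only that the plot was made.

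It is also fair to say that an omnibus test before taxon-level tests is partly a matter of preference, and that a test added now cannot be pre-specified.

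**Conclusion.** The point holds in a limited form. SAP section 3 specifies no between-arm test of overall community composition, and its only between-arm microbiota test works one OTU at a time in 14 v 9 people. A reader might infer that the trial cannot answer Hypothesis 1. That goes too far, because a corrected OTU interaction could support it. What is missing is an omnibus answer, and that matters for small shifts spread over many taxa.

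In the most favourable small-shift setting simulated, detection is about 13–17 % by OTU tests against 87–88 % by an omnibus test. With correlated OTUs the contrast is nearer 16 % against 41 %, and for large shifts there is practically none. These figures rest on an assumed OTU count, normal change scores and simple *t*-tests. DESeq2 is a count model and UniFrac weights taxa by phylogeny, so the real contrast may differ. The permutation test also assumes that selection into the sequenced subset was unrelated to arm. It is worth making the change, but the stated analyses do not become invalid without it.

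**What to change.** Add to SAP section 3 a PERMANOVA on the weighted UniFrac distances already calculated:

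- Terms: subject as blocking term, time, and time-by-arm.
- Time-by-arm P-value: permute arm labels across the 23 people, keeping each person's two samples together. A large random sample of the 817,190 assignments is enough.
- Report R-squared with the P-value.
- Label the test post hoc, because the SAP was written after the trial was completed.
- Report it alongside the DESeq2 interaction results. It should neither replace them nor be promoted to the deciding test of Hypothesis 1.
- State that no conclusion about arm differences is drawn from the PCoA plot alone.

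The cost is a few lines of R and no new samples. SAP section 2.5 says that microbiota results could not be supplied because they are complex to present; one R-squared with its P-value would be a compact result to supply. The downside is one more post hoc test. With 14 v 9 people, a null result would not show that there is no effect, and the report should say so.
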